Tumor assessments: Tumor assessments will be performed at baseline and every eight (8) weeks thereafter until completion of the protocol-specified study treatment, and 30 days after the last dose of nivolumab. Disease status will be assessed using both RECIST 1.1 and modified irRC (assessments will be performed at specified time points). Serum alanine aminotransferase (ALT) levels will be assessed on day 1 of each cycle. The ALT level must be within the acceptable range before administering the study drug combination, and dosing will be discontinued either temporarily or permanently for any patient who has a severe cytokine reaction, elevated ALT level ($> 5 \times$ upper limit of normal [ULN]), or any other Grade 4 or greater adverse effect.

[figure not shown]
5. Study design

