5.1 Description of study design

This is a phase II window of opportunity study evaluating the efficacy and toxicity of SBRT and in situ gene therapy followed by nivolumab in metastatic squamous and non-squamous NSCLC and metastatic uveal melanoma.

Figure 1: Study design

PHASE II WINDOW OF OPPORTUNITY TRIAL OF STEREOTACTIC-BODY RADIATION THERAPY AND IN SITU GENE THERAPY FOLLOWED BY NIVOLUMAB IN METASTATIC SQUAMOUS OR NON-SQUAMOUS NON-SMALL CELL LUNG CARCINOMA AND METASTATIC UVEAL MELANOMA.
ENSIIGN TRIAL

6. Treatment

ADV/HSV-tk (5×10^{11} viral particles) in a 2-mL total volume will be injected intratumorally on day 0 of the study. **Valacyclovir** will be orally administered at a dose of 2 g three times daily (t.i.d.) for 14 days. For patients with serum creatinine level between $1.6-2.0 \times$ ULN, valacyclovir dose will be reduced 50% (i.e., 1 g t.i.d.). Valacyclovir treatment will be administered 24 hours after the gene vector injection from day 1 to day 15 of the study.

SBRT of 30 gray (Gy; 6 Gy X 5 fractions) will be administered over 2 weeks from day 2 to day 14 of the study.

Nivolumab (480 mg) will be administered intravenously over 30 minutes every 4 weeks (± 1 day) starting on day 17 of the study and continuing until disease progression, unacceptable toxicity, or up to 12 months in patients without disease progression.

Immune-mediated complications of nivolumab will be defined as immunological reactions requiring the use of corticosteroids. Grade 2 or greater immune-mediated complications must be managed with 1 to 2 mg/kg/day prednisone equivalents, followed by corticosteroid taper. Permanently discontinue nivolumab for severe (Grade 3) or life-threatening (Grade 4) immune-mediated complications and withhold nivolumab until resolution of moderate (Grade 2) immune-mediated complications. Based on the severity of the event, consider restarting nivolumab after completion of corticosteroid taper.

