^jRelapsed/refractory and/or metastatic patients will be evaluated with /CT scan of the thorax, abdomen, and pelvis at screening, every eight (8) weeks thereafter until completion of the protocol-specified treatment and/or at the discretion of the treating physician, at EOT, and when clinically indicated. For patients with equivocal CT scan results, PET scan will be performed.

^kIn patients with accessible tumor, biopsies will be conducted at Visit 1, after the first dose of nivolumab (\pm 2 days), and if the patient progresses while on treatment, before the patient starts the new treatment.

Banked tumor tissue obtained as part of the patient's standard care and additional biopsies will be evaluated at a later time for assessment of Th1 response (IL-1, IL-2, IL-6, IL-12, IFN- α , and GM-CSF) and TILs before and after ADV/HSV-tk + Valacyclovir therapy.

^lBlood samples for correlative studies will be collected at screening, after the first dose of nivolumab (\pm 2 days), and at the end of Cycle 2 of nivolumab. An additional sample will be collected from patients whose disease progresses while on treatment. Blood samples will be collected into standard vacutainer tubes (3 green top tubes). Samples will be evaluated for profile of circulating suppressor and effector immunocytes and cytokines.

^mADV/HSV-tk will be injected intratumorally at 5×10^{11} viral particles in a 2-mL total volume on day 0 of the study. The study coordinator will dispense the 14-day quantity of Valacyclovir on Day 0 of the study. The patient will be instructed to take Valacyclovir (2 g) orally t.i.d. for 14 days (day 1 to day 15 of the study). NOTE: For patients with serum creatinine level between 1.6–2.0 \times ULN, valacyclovir dose will be reduced 50% (i.e., 1 g t.i.d.).

SBRT of 30 Gy (6 Gy X 5 fractions) will be administered over 2 weeks from day 2 to day 14 of the study. Nivolumab (480 mg) will be administered intravenously over 30 minutes every 4 weeks (\pm 1 day) starting on day 17 (\pm 1 day) of the study and continuing until disease progression, unacceptable toxicity, or up to 12 months in patients without disease progression.

ⁿAEs and SAEs will be captured from the time of informed consent signing up to and including 30 days after the final dose of nivolumab. Study treatment-related SAEs occurring beyond 30 days after the last dose of nivolumab and any study patient death should also be reported.

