12.3 Modified irRC, derived from RECIST 1.1¹⁹¹

This new classification is based on recent clinical studies showing delays in tumor regression or stabilization with cancer immunotherapies. For the ENSIGN trial, the concepts of the irRC are combined with RECIST 1.1 to come up with the modified irRC, which uses unidimensional measurements. For modified irRC, only target and measurable lesions are taken into account. In contrast to RECIST 1.1, the modified irRC criteria (a) require confirmation of both progression and response by imaging at eight 8 weeks after initial imaging (evidence of cancer progression within the first 3 months on bone scan only should be interpreted with extreme caution due to risk of tumor flare) and (b) do not necessarily score the appearance of new lesions as PD if the sum of the diameters of target lesions (minimum of 10 mm per lesion, maximum of 5 target lesions, maximum of 2 per organ) and measurable new lesions does not increase by $\geq 20\%$. The same assessment method and technique should be used to characterize each identified and reported target lesion(s) at baseline, during the trial, and at EOT. All measurements should be recorded in metric notation. The modified irRC based on RECIST 1.1 are displayed below. Modified irRC are defined as follows:

- New measurable lesions: Incorporated into tumor burden.
- New non-measurable lesions: Do not define progression but preclude irCR.
- Overall irCR: Complete disappearance of all lesions (whether measurable or not) and no new lesions. All measurable lymph nodes also must have a reduction in short axis to 10 mm or less.
- Overall irPR: $\geq 30\%$ decrease in the sum of the longest diameters of target and new measurable lesions.
- Overall irSD: Neither sufficient shrinkage to qualify for irCR or irPR (compared to baseline) nor sufficient increase to qualify for irPD (compared to nadir), using the sum of the longest diameters of target and new measurable lesions.
- Overall irPD: $\geq 20\%$ increase in the sum of the longest diameters of target and new measurable lesions increases (compared to nadir), confirmed by a repeat, consecutive observation at least 6 weeks (normally it should be done at 8 weeks) from the date first documented.

Documentation of immune-related PD (based on modified irRC) does not mandate discontinuation of the study treatment even after irPD is confirmed with CT scan 6 weeks after the initial observation of irPD.

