Statistical Analysis: DoR, OS, PFS, and CBR will also be analyzed. Safety profiles will be assessed through summaries of AEs, SAEs, AEs leading to treatment discontinuation, and treatment-related death. The safety analysis will report the frequency of all AEs and laboratory abnormalities as well as the frequency of dose interruptions and toxicity-related treatment discontinuation. Toxicity rates will be presented using the worst NCI CTCAE grade per patient.

Data Management: CRFs will be designed and utilized to capture all patient data. An electronic database will be designed to store patient CRFs. Data quality control will be performed regularly by the research coordinator/research nurse to ensure timely, accurate, and complete patient data collection. Queries will be generated and resolved prior to generation of interim and final summary reports.

16 Protocol amendments or changes in study conduct

Any change or addition to this protocol requires a written protocol amendment that must be reviewed by the investigator, local IRB, and FDA before implementation. Amendments significantly affecting the safety of subjects, the scope of the investigation, or the scientific quality of the study require additional approval by the IRB at each study center and the FDA. Examples of amendments requiring such approval are:

1. Increases in drug dose or duration of exposure of subjects
2. Significant changes in the study design (e.g., addition or deletion of a control group)
3. Increases in the number of invasive procedures
4. Addition or deletions of a test procedure required for safety monitoring

These requirements for approval should in no way prevent any immediate action from being taken by the investigator in the interests of preserving the safety of all patients included in the trial. The IRB must be notified if immediate changes are made to the protocol by the investigator for safety reasons. Amendments affecting administrative aspects of the study do not require formal protocol amendments but will require IRB approval.

17 Data safety monitoring

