Appendix D: Modified irRC, derived from RECIST 1.1

Overall responses derived from changes in index, non-index, and new lesions

Measurable Response	Non-Measurable Response		Overall Response Using Modified irRC
Index and New, Measurable Lesions (Tumor Burden)	Non-Index Lesions	New, Non-Measurable Lesions	
Decrease 100%	Absent	Absent	irCR*
Decrease 100%	Stable	Any	irPR*
Decrease 100%	Unequivocal progression	Any	irPR*
Decrease \geq 30%	Absent / Stable	Any	irPR*
Decrease \geq 30%	Unequivocal progression	Any	irPR*
Decrease < 30% to increase < 20%	Absent / Stable	Any	irSD
Decrease < 30% to increase < 20%	Unequivocal progression	Any	irSD
Increase \geq 20%	Any	Any	irPD

* Assuming that the response (irCR and irPR) and progression (irPD) are confirmed by a second, consecutive assessment at least 4 weeks apart (normally it should be done 6 weeks apart).

Key Milestones:

FPFV / First Dose:

LPLV / Last Subject completed:

Database Lock:

Final Report:

Sponsoring Department: HMHCC &HMHRI

Prepared by: _____

Date _____

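### The imaging schedule does not assure the scan that Section 12.3 needs to confirm irPD once nivolumab stops, and no rule says how an unconfirmed increase is analysed

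*Combined protocol and SAP*

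**What the plan says.** **Confirmation.** Three statements of the interval stand in the protocol:

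- Section 12.3, opening text: the modified criteria "require confirmation of both progression and response by imaging at eight 8 weeks after initial imaging".
- Section 12.3, irPD definition: the increase must be "confirmed by a repeat, consecutive observation at least 6 weeks (normally it should be done at 8 weeks) from the date first documented".
- Appendix D, footnote, which covers irCR, irPR and irPD: "confirmed by a second, consecutive assessment at least 4 weeks apart (normally it should be done 6 weeks apart".

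**Imaging.** Section 4 (Tumor assessments) schedules scans at baseline and then "every eight (8) weeks thereafter until completion of the protocol-specified study treatment, and 30 days after the last dose of nivolumab". The footnote to the visit table in Section 11 adds CT "and/or at the discretion of the treating physician, at EOT, and when clinically indicated". Section 7 (Study Duration) gives a follow-up of 6 months or until progression, with no imaging schedule.

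**Treatment.** Nivolumab starts on day 17 and is given every 4 weeks, "continuing until disease progression, unacceptable toxicity, or up to 12 months in patients without disease progression" (Section 6). The criteria for that progression are not named. Section 12.3 says that irPD, even when confirmed, does not oblige the investigator to stop treatment.

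**Analysis.** On these endpoints Section 15.1 says only that "DoR, OS, PFS, and CBR will also be analyzed". No event definition, censoring rule, composition of CBR or choice between RECIST 1.1 and irRC is given. Nothing says how to treat a first increase of 20% or more that is never re-imaged.

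**The concern.** A definition that requires a later scan works only if the schedule supplies that scan, or if a rule covers its absence. Here the schedule supplies it while treatment continues, but not reliably once treatment stops.

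Missing confirmation is unlikely to be random. Patients who deteriorate quickly, stop, or die are the least likely to be re-imaged. If their first increase is disregarded, an irRC-based PFS would censor them or date their event at death instead of at progression, and both lengthen the estimate. The same applies to DoR when a responder later progresses and stops. Because the plan is silent, the choice could be made after the data are seen. In cohorts of 16 and 9, each such choice is visible in the result.

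**Working it through.** **1. The plan's own figures.** The only stated quantities are the ORR powers in Section 15.1. Exact one-sample binomial calculations reproduce them:

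- NSCLC, n = 16, success at 3 or more responses: one-sided alpha 0.0113 at 3%, power 0.8029 at 25% (stated 80.3%).
- Uveal melanoma, n = 9, success at 2 or more: alpha 0.0282 at 3%, power 0.8040 at 30% (stated 80.4%).

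Neither depends on how irPD is confirmed. The plan gives no figure for PFS, DoR or CBR.

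**2. Gap when nivolumab stops at the first progression scan.** Doses fall on days 17, 45, 73, 101 and so on. Let d be the days from the last dose to the progression scan (0 to 27). The last scheduled scan is 30 days after the last dose, so the gap is 30 − d.

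| 8-week clock starts on day | First scan after a dose | Last dose | Last scheduled scan | Gap (days) |
|---|---|---|---|---|
| −28 | 28 | 17 | 47 | 19 |
| −14 | 42 | 17 | 47 | 5 |
| −7 | 49 | 45 | 75 | 26 |
| −1 | 55 | 45 | 75 | 20 |
| 0 | 56 | 45 | 75 | 19 |
| 17 | 73 | 73 | 103 | 30 |

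Doses repeat every 28 days and scans every 56, so each gap recurs at later scans. The maximum is 30 days (d = 0). A final scan 5 days late makes it 35. Adding a further 5 days for an early progression scan gives an outer bound of 40. All are below 6 × 7 = 42 days.

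**3. Appendix D's 4 weeks.** 30 − d ≥ 28 requires d ≤ 2, which is 3 of the 28 possible offsets. With the final scan 5 days late, 35 − d ≥ 28 requires d ≤ 7, or 8 of 28.

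**4. If treatment continues.** The next 8-weekly scan is 56 days later and meets every version of the interval. If exactly one more dose is given, the final scan comes 28 + 30 − d = 58 − d days after the progression scan. For a day-56 scan (d = 11) that is 47 days, which is enough. For a day-42 scan (d = 25) it is 33 days, which is not. The 6-week rule is met when d ≤ 16.

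**5. What the missing rule leaves open.** Take an invented patient whose sum rises from 60 to 87 mm on day 56 (27/60 = +45%), who stops nivolumab, is last scanned on day 75 and dies on day 150.

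- RECIST 1.1 (Section 12.2): progression on day 56. No confirmation is needed for a target-lesion increase of this size.
- Modified irRC, literally: no irPD. PFS could be censored at day 75, counted at death on day 150 (150/56 = 2.7 times as long), or dated back to day 56.
- irRC-based CBR: irSD does not fit, because Appendix D's irSD rows stop below a 20% increase. The patient has no category.

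**6. Scale.** One patient reclassified moves CBR by 1/16 = 6.25 points or 1/9 = 11.1 points. For PFS, suppose event times are exponential and a share f of events is censored at about the event time. The estimated hazard falls by the factor (1 − f) and the median rises by 1/(1 − f): 1.11 at f = 10%, 1.33 at 25%, 2.0 at 50%. The documents do not give f.

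**The case against.** The strongest reply is that confirmation is required, not impossible. Section 12.3 itself calls for imaging at 8 weeks, and the visit-table footnote allows CT at discretion or when indicated. Section 10 bars other anticancer therapy until progression is documented by modified irRC, so the protocol presumes that documentation happens. The gap also depends on stopping at the first, unconfirmed increase. Section 12.3 does not require that, and Section 12.4 does not list progression as a reason for withdrawal. RECIST 1.1 is applied in parallel, and nothing ties PFS, DoR or CBR to irRC.

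All of this stands, and it rules out the stronger conclusions that a reader might draw:

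- *That such patients never become irPD.* An unscheduled scan or continued treatment can confirm it, and Appendix D's shorter minimum occasionally lets the final scheduled scan do so.
- *That irRC-based PFS, DoR and CBR are inflated.* The plan does not say that these endpoints use irRC. For CBR the patient is unclassified, not counted as a benefit. DoR concerns only responders, so patients who progress at the first scan do not enter it.
- *That about 7 of 16 and 3 to 4 of 9 patients are affected.* These counts come from the PFS medians of 2.3 and 2.6 months cited in Section 1.1. With 8 weeks taken as 1.84 months, 1 − 2^(−1.84/2.3) = 43% and 1 − 2^(−1.84/2.6) = 39%. They assume exponential times and that every progressor stops at that scan, and they count every PFS event as a 20% increase. The NSCLC cohort here must also have progressed after immunotherapy. They are ceilings under assumptions, not estimates.

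The reply does not remove the mismatch. Stopping at progression is foreseen in Section 6, and Section 12.4 withdraws patients from treatment and procedures for several toxicities. A patient with an unconfirmed increase at that point has no planned route to confirmation and no analysis rule.

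**Conclusion.** The point holds as a mismatch between the irPD rule and the imaging schedule, together with a missing analysis rule. For a patient who receives no dose after the first progression scan, no scheduled scan meets the 6-week minimum: the gap is at most 30 days, or about 35 to 40 with windows, against 42. Under Appendix D's 4 weeks a scheduled scan would confirm in only a few timings.

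The consequence is a risk of upward bias in any irRC-based PFS, and in DoR among responders, plus an undefined status for irRC-based CBR. The size of the bias cannot be computed from the documents. It depends on how many patients stop at a first increase, how many have unscheduled scans, and which unstated rule is applied. RECIST 1.1 results and the power for the primary ORR are unaffected. These are secondary endpoints with no stated test, so the matter should be corrected but does not undermine the design.

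**What to change.** 1. **Sections 12.3 and 15.1: add an analysis rule.** Suggested text: *For irRC-based PFS, DoR and CBR, a first increase of 20% or more with no later qualifying scan, whether because of treatment stop, death, new anticancer therapy or no imaging, counts as irPD on the date it was first documented. It is set aside only if a later qualifying scan shows that the increase was not sustained. Confirmed irPD is dated to the first scan.*
2. **Section 12.3 and Appendix D: reconcile the interval.** Choose one among 8 weeks, at least 6 weeks and at least 4 weeks, so that a qualifying scan has one meaning. The Appendix D footnote also governs irCR and irPR, so this should be settled before response data are read.
3. **Section 15.1: name the criteria.** State whether RECIST 1.1, modified irRC or both define PFS, DoR and CBR.

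Sections 6 and 12.3 should also be reconciled on what progression means for continuing nivolumab. That is a clinical decision, and the analysis rule works under either reading.

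The cost is a few sentences, with no added scans and no change to treatment. The downside is that some patients with pseudo-progression who stop early will count as progressed, so irRC-based PFS and CBR will look slightly less favourable.

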12.4 Withdrawal of subjects from study

Subjects must be withdrawn from the trial (treatment and procedures) for the following reasons:

- Therapy will be discontinued temporarily or permanently for cytokine release syndrome.
- Therapy will be discontinued temporarily or permanently for elevated ALT ($> 5 \times$ ULN).
- Any Grade 4 or greater AE.

- Severe (Grade 3) or life-threatening (Grade 4) immune-mediated complications.
- TTP/HUS.
- Neurotoxicity (e.g., encephalopathy, seizures).
- Dose interruption that exceeds 21 days.
- Subject withdraws consent from study treatment and study procedures. A subject must be removed from the trial at his/her own request or at the request of his/her legally acceptable representative. At any time during the trial and without giving reasons, a subject may decline to participate further. The subject will not suffer any disadvantage as a result.
- Subject is lost to follow-up.
- Death.

Any subject removed from the trial will remain under medical supervision until discharge or transfer is medically acceptable. In all cases, the reason for withdrawal must be recorded in the CRF and the subject's medical records.

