Patients whose treatment is interrupted or permanently discontinued due to an AE including abnormal laboratory value must be followed at least once a week for 4 weeks and subsequently at 4-week intervals until resolution or stabilization of the event, whichever comes first. Dose interruptions should be reported on the appropriate Dosage Administration case report form (CRF). The maximum time allowed for toxicity-related treatment interruption is 21 days (3 weeks) from the intended dosing day. If interruption is > 3 weeks, the patient must be discontinued from the study treatment. However, the patient will continue to be followed for toxicity.

7. Population

Metastatic NSCLC: Male or female patients aged ≥ 18 years with histologically or cytologically confirmed metastatic squamous or non-squamous NSCLC whose disease has progressed after a platinum-based chemotherapy and after a single-agent immunotherapy. Patients with *EGFR* or *ALK* genomic tumor aberrations should have disease progression on FDA-approved therapy for these aberrations prior to receiving nivolumab. The investigator or designee must ensure that the patient meets all the inclusion and none of the exclusion criteria before being offered enrollment in the study.

Metastatic Uveal Melanoma: Male or female patients aged ≥ 18 years with histologically or cytologically confirmed metastatic uveal melanoma that is immunotherapy naïve.

Study Duration:

After administration of ADV/HSV-tk + Valacyclovir followed by SBRT, nivolumab will be given every 4 weeks from day 17 until disease progression, unacceptable toxicity, or up to 12 months in patients without disease progression. Patients will be followed up for 6 months or until disease progression, whichever occurs first. Patients will be assessed for AEs up to and including 30 days after the last treatment dose.

Safety Criteria:

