Cimetidine and probenecid increase the area under the curve (AUC) of acyclovir and reduce acyclovir renal clearance after Valacyclovir administration (1000 mg). However, no dosage adjustment is necessary at this dose because of the wide therapeutic index of acyclovir.

Drug-Food Interactions: There is no known interaction with food.

Drug-Herb Interactions: Interactions with herbal products have not been established.

Drug-Laboratory Test Interactions: Interactions with laboratory tests have not been established.

Dosage and administration:

The recommended dose for the ENSIGN trial is 2 g orally t.i.d. for 14 days (day 1 to day 15). This dose has been calculated to give a similar AUC as 10 mg/kg of intravenous acyclovir administered every 8 hours. This is the same dose regimen used in a previous phase I clinical trial of ADV/HSV-tk plus acyclovir and topotecan in patients with recurrent ovarian cancer.⁸¹ NOTE: For patients with serum creatinine level between 1.6–2.0 × ULN, valacyclovir dose will be reduced 50% (i.e., 1 g t.i.d.).

Recommended Dose and Dosage Adjustment

Patients who develop signs of TTP/HUS or neurotoxicity (e.g., encephalopathy, seizures) will be removed from treatment.

Patients with acute or chronic renal impairment: Caution is advised when administering Valacyclovir to patients with impaired renal function. Adequate hydration should be maintained.

Pharmacokinetic and safety evaluations following administration of oral valacyclovir hydrochloride have been performed in patients with renal impairment and volunteers with end-stage renal disease managed by hemodialysis. Valacyclovir dosing in patients with renal impairment is shown in Table 4.

Table 4. Valacyclovir dosing in patients with renal impairment

Creatinine Clearance (mL/min)				
	> 50	30 to <50	10 to <30	< 10
Herpes Zoster	1000 mg every 8 hours†	1000 mg every 12 hours	1000 mg every 24 hours	500 mg every 24 hours
Recurrent Episodes of Genital Herpes	500 mg every 12 hours†	500 mg every 12 hours†	500 mg every 24 hours	500 mg every 24 hours
Suppression of genital herpes for immunocompetent patients	1000 mg every 24 hours†	1000 mg every 24 hours†	500 mg every 24 hours	500 mg every 24 hours
Alternate dose for immunocompetent patients with less than or equal to 9 recurrences/year	500 mg every 24 hours†	500 mg every 24 hours†	500 mg every 48 hours	500 mg every 48 hours
HIV-infected patients	500 mg every 12 hours†	500 mg every 12 hours†	500 mg every 24 hours	500 mg every 24 hours

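### Section 12.4 withdraws patients from the whole trial for toxicities that other sections handle by holding or stopping treatment, so planned scans and follow-up may end for treatment-related reasons

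*Combined protocol and SAP*

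**What the plan says.** Section 12.4 opens with a mandatory rule covering treatment and procedures alike: "Subjects must be withdrawn from the trial (treatment and procedures) for the following reasons". Ten reasons follow. Three (consent withdrawal, loss to follow-up, death) properly end participation. The other seven are toxicity events. The first of these reads: "Therapy will be discontinued temporarily or permanently for cytokine release syndrome"; the ALT item has the same form. For a removed patient, 12.4 keeps only medical supervision until it is acceptable to discharge or transfer the patient.

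Elsewhere the same events lead to action on treatment:

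- Section 4 (Tumor assessments): "dosing will be discontinued either temporarily or permanently for any patient who has a severe cytokine reaction". The sentence goes on to cover ALT above 5 × ULN and other Grade 4 or higher effects.
- Section 6: "Permanently discontinue nivolumab for severe (Grade 3) or life-threatening (Grade 4) immune-mediated complications".
- Section 9.2: "Patients who develop signs of TTP/HUS or neurotoxicity (e.g., encephalopathy, seizures) will be removed from treatment".
- Section 6, on a long interruption: "The maximum time allowed for toxicity-related treatment interruption is 21 days (3 weeks) from the intended dosing day"; beyond that, "the patient must be discontinued from the study treatment. However, the patient will continue to be followed for toxicity". Sections 7 and 12 repeat this rule.

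Section 7 (Study Duration) plans follow-up with no exception for toxicity: "Patients will be followed up for 6 months or until disease progression, whichever occurs first". The Glossary says that stopping treatment is not necessarily withdrawal, and that a withdrawn patient may still be followed for progression or survival.

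**The concern.** Two instructions apply to the same patient and nothing says which governs. Someone dealing with an ALT above 5 × ULN finds mandatory withdrawal in 12.4 and a possible temporary hold in Section 4. Patients with the same event could be handled differently, and those handled under 12.4 would stop contributing tumor data because of a toxicity.

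The primary endpoint is ORR under RECIST 1.1 and modified irRC, and Section 12.3 requires a confirming scan for a modified irRC response. A patient taken off procedures before the first post-baseline scan has no scheduled response assessment. One removed between a first response and its confirmation has no confirmed modified irRC response. DoR and PFS lose follow-up in the same way. The cohorts have 16 and 9 patients, and Section 15 does not say how such patients count in the ORR.

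The ALT trigger shows how this could arise. Section 8.1 admits patients with liver metastases and transaminases up to 5 × ULN, 12.4 is triggered above 5 × ULN, Section 9.1 lists raised liver enzymes as a possible vector effect, and Section 1.1 gives the liver as the most frequent metastatic site in uveal melanoma (95%). This shows that the event is possible; it does not give its frequency.

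**Working it through.** **Step 1. The rules side by side.** Section 4's severe cytokine reaction is taken to be the same event as 12.4's cytokine release syndrome.

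| Event | Section 12.4 | Elsewhere |
|---|---|---|
| Cytokine release syndrome | Lead-in: leave trial. Item: therapy stopped, temporarily or permanently | Section 4: dosing stopped, temporarily or permanently |
| ALT > 5 × ULN | As above | Section 4: as above |
| Grade 4+ AE | Leave trial | Section 4: as above |
| Grade 3–4 immune-mediated event | Leave trial | Section 6: nivolumab stopped permanently |
| TTP/HUS, neurotoxicity | Leave trial | Section 9.2: off treatment |
| Interruption > 21 days | Leave trial | Sections 6, 7, 12: off treatment, toxicity follow-up continues |

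Every toxicity trigger has a treatment-level counterpart. For cytokine release syndrome and ALT the conflict also lies inside 12.4, since a temporary stop of therapy cannot coexist with mandatory exit from the trial.

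**Step 2. What literal use of 12.4 removes.**

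- *Temporary hold* (possible for the Section 4 events): treatment ends, and with it all later on-treatment scans.
- *Permanent stop*: the 8-weekly scans end with protocol treatment anyway (Sections 4, 7, 11, 12). At risk are the EOT/30-day scan, any discretionary or confirmatory scan, and the Section 7 follow-up.

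**Step 3. Scan count for the temporary hold (illustration, a maximum).** Assume scans every 56 days from day 0, and nivolumab from day 17 for 365 days.

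- Last treatment day: 17 + 365 = 382.
- Planned 8-weekly scans: 382 / 56 = 6.8, so 6 (days 56, 112, 168, 224, 280, 336).
- Trigger before day 56: up to 6 scans lost. Trigger between days 56 and 112: up to 5.
- Under the other sections: a hold of at most 21 days is shorter than the 56-day interval, so at most one scan date falls inside it, and nothing cancels that scan.

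These counts apply to a patient who would otherwise stay on treatment for the full 12 months.

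**Step 4. The plan's own power figures, and sensitivity at the cut-off (illustration).** Inputs are from Section 15.1: one-sided 0.05; NSCLC n = 16, 3% against 25%; uveal melanoma n = 9, 3% against 30%. The cut-off is the smallest r with P(X ≥ r | n, p0) ≤ 0.05, X binomial.

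| Cohort | Cut-off r | P(X ≥ r) at 3% | Power | Stated power | P(X ≥ r − 1) at 3% |
|---|---|---|---|---|---|
| NSCLC | 3/16 | 0.0113 | 0.803 | 80.3% | 0.0818 |
| Uveal melanoma | 2/9 | 0.0282 | 0.804 | 80.4% | 0.2398 |

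The stated power reproduces. Exactly at the cut-off, one responder fewer moves the one-sided p-value from 0.011 to 0.082, or from 0.028 to 0.240. That holds for a responder lost for any reason and does not measure the effect of 12.4.

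**The case against.** The strongest reply is that sites would not read 12.4 literally. The cytokine and ALT items are full sentences about therapy that do not fit the lead-in, which suggests pasted text. Sections 6, 7 and 12 set follow-up for patients whose treatment is interrupted or stopped, which presupposes that they remain in the study. The Glossary permits progression or survival follow-up after withdrawal. This is a fair account of the likely intent, but it does not settle the rule. The Glossary permits that follow-up without requiring it, while 12.4 is mandatory, names procedures, and keeps only medical supervision.

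Several stronger readings are tempting, and the documents do not support them:

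- *Safety follow-up stops.* Sections 6, 7 and 12 require toxicity follow-up, and AEs are collected to 30 days after the last dose.
- *The word procedures costs six scans.* The count is a maximum. It arises largely because literal 12.4 also ends treatment, with which the 8-weekly scans end.
- *Elsewhere these events are only a pause of up to 21 days.* Section 4 allows a permanent stop, and the remaining triggers mean stopping treatment or nivolumab elsewhere too.
- *The EOT scan is certainly lost.* The schedule ties a tumor assessment to EOT whatever the reason for stopping, and the Glossary's entry on stopping participation contemplates a final evaluation visit. The scan is at risk, no more.
- *The ORR test would change its result.* That needs a cohort exactly at its cut-off and a would-be responder with no countable response before the trigger who is scored as a non-responder. Section 12.3 contrasts RECIST 1.1 with the confirmation that modified irRC demands, so a RECIST response already recorded would stand.

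It is also true that Section 7 sets no imaging schedule for the 6-month follow-up, so imaging for DoR and PFS thins out after treatment regardless of 12.4.

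**Conclusion.** The inconsistency is real and no other section resolves it. For seven toxicity triggers, 12.4 orders exit from treatment and procedures where Sections 4, 6, 7, 9.2 and 12 act on treatment only. Followed as written, it converts a permitted hold into the end of treatment and its scans, and after a permanent stop it endangers the remaining scans and the planned follow-up. ORR, DoR and PFS can then lose data for reasons related to treatment.

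The size cannot be estimated: the documents give neither the frequency nor the timing of the triggers on this regimen. The scan counts rest on the assumed 56-day grid and 12 months of treatment. The cut-off p-values are correct but generic to cohorts this small. Neither shows that the trial's result would be affected. The stated power figures are not in question. The case for the change rests on a mandatory rule that contradicts the rest of the protocol and is cheap to repair.

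**What to change.** Split Section 12.4 into two lists.

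- **(a) Events that hold or end study treatment:** cytokine release syndrome, ALT above 5 × ULN, Grade 4 or higher AE, Grade 3–4 immune-mediated event, TTP/HUS, neurotoxicity, interruption over 21 days. State that these patients keep the toxicity follow-up of Sections 6, 7 and 12, the tumor assessments already planned (8-weekly while treatment is only held; EOT and 30-day after a permanent stop, plus any discretionary scan), and the Section 7 follow-up.
- **(b) Events that end participation:** consent withdrawal, loss to follow-up, death.

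As a supporting clarification, add one sentence to Section 15 saying that patients in (a) stay in the ORR denominator.

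The cost is a rewording of 12.4 and that one sentence. It adds no scan beyond those already planned and changes neither the schedule nor the sample size. Continuing 8-weekly imaging after a permanent stop would be a separate, optional change to Sections 4, 7, 11 and 12; it is not needed here.
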